Visit 3, 4 and 5: 5 HV who completed visits 1 and 2 will be recruited to undergo development of TMS stimulation protocol at Duke BSRC. TMS Stimulation will be provided up to 20 minutes (at 10Hz) with a writing sample during stimulation. Subjects will also perform a writing assessment before and after each stimulation block. An fMRI will be performed after completion of each TMS stimulation session.

20 focal hand dystonia subjects who completed visits 1 and 2 will also be recruited to undergo 3 visits of TMS stimulation at Duke Brain Stimulation Center. The 3 visits will each be 1 week apart. 2 visits will involve active TMS and 1 visit will be sham TMS. During one of the active TMS visits, TMS coil will be applied to the premotor cortex for brain stimulation while during the other active TMS visit, TMS coil will be applied to the primary sensory cortex. TMS stimulation protocol will consist of 10Hz stimulation for up to 20 minutes with a writing task during the stimulation block. Subjects will undergo a writing assessment before and after each stimulation block and complete TMS side effects survey. Writing task is different from writing assessment in that writing task will only be used as part of the investigational therapy while writing assessment will be data collected for outcomes measures. fMRI will be performed after completion of each of the 3 TMS visits.

Background & Significance

- Should support the scientific aims of the research

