 3. Healthy volunteers will undergo TMS stimulation protocol development. Subjects will receive 10Hz active stimulation at premotor cortex during one visit and primary sensory cortex during another visit for up to 20 minutes with stimulation intensity up to 120% of resting motor threshold which is within the published safety guidelines (47) and based on previously published protocol used in multiple human studies(13–16). The resting motor threshold is a baseline stimulation intensity determined using the protocol in step 2. Additional stimulation parameters including duration of continuous stimulation, interstimulus interval, stimulation intensity, orientation of magnetic coil, biphasic or monophasic stimulation will be developed with healthy volunteers based on the published safety guidelines(47), writing assessment (includes writing and non-writing sampling) and feasibility within 20 minutes stimulation paradigm.
 4. WC subjects will undergo TMS stimulation visits 3, 4 and 5. 2 visits will include active TMS stimulation while the remaining one visit will be a control sham stimulation. Of the 2 active TMS stimulation visits, subjects will receive TMS at premotor cortex during one visit and at primary sensory cortex during the other active TMS visit. The dosage of active stimulation will be 10Hz for up to 20 minutes with resting motor threshold up to 120% which is within the published safety guidelines (47) and based on previously published protocol used in multiple human studies(13–16). During both active and sham stimulation blocks, subjects will be asked to perform a writing task of writing a diverse paragraph as an online stimulation task. The stimulation block will be preceded and followed by a writing assessment and TMS acute side effects survey to assess safety of the stimulation. Visit 3, 4, and 5 will occur 1 week apart. Subject will undergo fMRI after each of the 3 TMS visits.

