Our preliminary analysis of the Duke patient population reveals sufficient population of FHD subjects to recruit for our study at Duke University. Our electronic patient database identifies 186 Duke patients with a specific diagnosis of organic writer's cramp (ICD 9 code 333.84). Because ICD 10 code does not have a specific writer's cramp diagnosis, we suspect that more cases are included within the ICD G24.9 (focal dystonia) group. Therefore, the primary care providers for all 837 subjects with either of these codes may be contacted by research coordinator for patient candidacy for this research study as detailed in Section 6 eIRB submission form.

Analysis and Statistics: [name] in the Department of Neurology, **[name] and [name] in the BERD core of the Statistics Department** will be **involved** the de-identified data **analysis** but will be not involved in collecting the data. Visit 1 data of handwriting metric differences between healthy participants and focal hand dystonia patients will establish writing metric sensitivity at our site and recalculate power analysis to adjust cohort sizes, or improve technique, as indicated for visits 2, 3, and 4. For Visit **3 -5**, a two-way ANOVA will be performed with groups (healthy vs dystonia) and stimulation type (task during vs after stimulation) as the main factor within subjects. A two-way repeated measures ANOVA will be conducted with stimulation type (task during vs after stimulation) and treatment type (sham vs active) as the main factors between subjects for each handwriting measure.

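### Both visit 3–5 ANOVAs use a during/after factor and omit the same-visit pre-stimulation assessment, so neither estimates the pre-to-post effect of active versus sham TMS

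*Combined protocol and SAP*

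**What the plan says.** The models are in the Analysis and Statistics paragraph of Data Analysis & Statistical Considerations. The first, for visits 3–5, has "groups (healthy vs dystonia) and stimulation type (task during vs after stimulation) as the main factor within subjects". The second reads "A two-way repeated measures ANOVA will be conducted with stimulation type (task during vs after stimulation", crossed with sham versus active, and is to be run on each handwriting measure. Neither sentence mentions the pre-stimulation assessment, a change score or a covariate.

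The design is in Design & Procedures, step 4. For patients, "2 visits will include active TMS stimulation while the remaining one visit will be a control sham stimulation", and "subjects will receive TMS at premotor cortex during one visit and at primary sensory cortex during the other active TMS visit". On the writing done within a session: "During both active and sham stimulation blocks, subjects will be asked to perform a writing task". On measurement: "The stimulation block will be preceded and followed by a writing assessment". Purpose of the Study schedules the same pre and post assessments for the healthy volunteers.

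Purpose of the Study also separates the two kinds of writing: "writing task will only be used as part of the investigational therapy while writing assessment will be data collected for outcomes measures". Step 5 of Design & Procedures repeats the distinction and adds that only the assessment is video-recorded, the video being the source of the blinded Writer's Cramp Rating Scale score. Purpose of the Study names visits 1 and 2 as the source of baseline measures for visits 3–5.

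**The concern.** A factor called stimulation type should separate kinds of stimulation. What varies between a patient's visits is premotor active, primary sensory active and sham. Whether the task comes during or after stimulation does not vary between visits.

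The factor therefore has to be read as time within a session. It then sets therapy writing, done while the coil is firing, against the post-stimulation outcome assessment. That differs from the comparison the session is built to give, which is writing before the block against writing after it, under active and under sham.

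At stake is the only behavioural analysis stated for visits 3–5. As written, its interaction can be null when stimulation helps, or positive when stimulation merely disturbs writing for the length of the block. The blinded rating-scale score has no during value and no stated visit 3–5 model.

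**Working it through.** **The plan's own figure.** The only power figure (60 subjects, 30% effect, alpha 0.05) comes without an SD, power or test, so it cannot be reproduced. Nothing below depends on it.

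**Factor levels against the schedule**

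| Level | As a stimulation condition | As a time point |
|---|---|---|
| During | Every active and sham block | Writing task, therapy only (Purpose of the Study; step 5) |
| After | No visit is described this way | Post-stimulation writing assessment |
| Before | Not in either model | Pre-stimulation writing assessment, collected but unused |

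**What each contrast estimates.** Let P, D and A be the mean active-minus-sham differences before, during and after the block, with positive values meaning better writing.

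- Planned interaction: A − D
- Planned sham-versus-active main effect: (D + A)/2
- Pre/post by treatment: A − P

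The effect sizes below are assumed. Rejection rates (in brackets) come from a paired-t simulation with 20 patients, one active and one sham visit each, 20,000 runs, subject SD 1, residual SD 0.5, and day-to-day SD of 0.25, 0.5 or 1.0, all assumed. They show direction only.

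| Scenario (P, D, A) | Interaction | Main effect | Pre/post by treatment |
|---|---|---|---|
| Equal benefit during and after (0, 1, 1) | 0 (about 5%) | 1 (81% to 100%) | 1 (about 99%) |
| Disturbance only during (0, −1, 0) | 1 (about 99%) | −0.5 (29% to 93%) | 0 (about 5%) |
| Benefit only after (0, 0, 1) | 1 (about 99%) | 0.5 (30% to 93%) | 1 (about 99%) |
| Disturbed during, better after (0, −1, 1) | 2 (about 100%) | 0 (about 5%) | 1 (about 99%) |

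**Cost to the main effect if benefit appears only after.** Let the during and after active–sham differences have equal variance s² and correlation r, and let the benefit be d.

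- After-only analysis: N is proportional to s²/d².
- Main effect: expectation d/2, variance s²(1+r)/2. N is proportional to [s²(1+r)/2]/(d²/4) = 2(1+r)·s²/d².
- Interaction: expectation d, variance 2s²(1−r). N is proportional to 2(1−r)·s²/d².

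| r | Main effect, N factor | Interaction, N factor |
|---|---|---|
| 0 | 2 | 2 |
| 0.5 | 3 | 1 |
| 1 | 4 | 0 (limit) |

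**Precision from the same-visit pre value.** With a common cross-visit correlation, the pre and post between-visit differences correlate at c = (ρ_same − ρ_cross)/(1 − ρ_cross). Used as a covariate, the pre value cuts the variance of the active–sham difference by c², ignoring the cost of estimating the slope. The documents give no correlations, so these are assumed:

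- ρ_same = ρ_cross: c = 0, gain 0%.
- 0.80 and 0.70: c = 0.10/0.30 = 0.33, gain 11%.
- 0.90 and 0.70: c = 0.20/0.30 = 0.67, gain 44%.

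A change score (pre/post factor) instead multiplies the variance by 2(1−c), which is 1.33 at c = 0.33 and 0.67 at c = 0.67. It targets the same effect but can lose precision, so the covariate form is preferable.

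A visit 1 or 2 baseline is one value per patient. It is the same under active and sham, so it cancels from their within-patient difference and cannot remove day-to-day variation.

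**The case against.** During and after do exist as time points in every session, and the tablet used for the writing task could capture data, so the factor can be computed. The protocol is also loose with its terms. It calls the visit 1 samples writing tasks, the sample size paragraph lists the writing task as an outcome measure (tagged to visit 1), and the fMRI paragraph speaks of TMS effects on writing-task performance. A task after stimulation may simply mean the post-stimulation assessment. Further, step 6 gives safety and feasibility as the use of visit 3–5 data, the sample is described as a pilot, and the pre and post data will be collected whatever the model says.

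Much of this stands. The factor is better described as a mislabelled time factor than as an impossible one, and the documents are not consistent about writing-task data. Nothing is lost for good. But two explicit definitions reserve the task for therapy, and the looser mentions do not give the pre-stimulation assessment a place in the models. A pilot label does not help either: the Data Storage and Management list asks for the statistical approach to be settled beforehand and stated clearly, and the opening objective is prolonged symptom improvement.

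**Conclusion.** The stated analysis is wrong as written. The during/after factor is not a stimulation condition, its during level conflicts with the protocol's own definition of outcome data, and neither model estimates pre-to-post change under active versus sham. This follows from the text and needs no assumed number.

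Three stronger readings are tempting and not supported:

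- *That the factor cannot be computed, or that no treatment effect can be estimated.* As a time factor it can be computed. The sham-versus-active main effect remains estimable, though it averages therapy writing with outcome writing and has no same-day baseline.
- *That the plan wastes a fixed fourfold number of patients.* The cost applies to the main effect only, when benefit appears only after stimulation, and is 2- to 4-fold under equal variances. Fourfold requires r = 1. In that same scenario the planned interaction carries the full effect and matches the after-only analysis at r = 0.5.
- *That the documents uniformly exclude writing-task data.* Two places do; the sample size and fMRI paragraphs are looser.

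The gain from a same-day covariate is uncertain: 0% if same-visit and cross-visit correlations are equal, and 11% to 44% at the assumed values. The safety and feasibility aims are unaffected.

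**What to change.** In the Analysis and Statistics paragraph:

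1. Patient model: drop the during/after factor. For each handwriting measure, use the post-stimulation writing assessment as outcome, the same-visit pre-stimulation assessment as covariate (a pre/post factor is an acceptable alternative), and treatment condition as a within-patient factor, since every patient is scheduled for both active targets and sham.
2. Healthy-versus-dystonia model: replace during/after with pre/post, which is collected in both groups.
3. Apply the patient model to the blinded Writer's Cramp Rating Scale score.
4. Label any analysis of writing during stimulation as exploratory.
5. Reconcile the use of writing task in the sample size and fMRI paragraphs with its definition in Purpose of the Study and step 5.

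The cost is analysis wording only. The pre and post assessments are already scheduled at every TMS visit. The change should be made before any visit 3–5 data are analysed.

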Furthermore, a meta-analysis of 5 TMS studies in WC dystonia subjects also demonstrated consistent albeit short-term benefit when TMS was applied at premotor cortex supporting its role in engaging dystonia brain circuitry(38–43) and supporting the idea that these regions are also linked by a common connection. A second potential cortical target is primary sensory cortex. Previous connectivity analysis in WC subjects demonstrated decreased functional connectivity between putamen and primary sensory cortex(27). Among the previous studies applying TMS to WC subjects, the study that showed the longest benefit (2weeks) targeted the primary sensory cortex(44). In this study, TMS stimulation will be applied to the premotor cortex during one visit and to primary sensory cortex during another visit to evaluate the optimal cortical target for modulating putamen activity using TMS in WC subjects.

Design & Procedures

- Describe the study, providing details regarding the study intervention (drug, device, physical procedures, manipulation of the subject or the subject’s environment, etc.). Discuss justifications for placebo control, discontinuation or delay of standard therapies, and washout periods if applicable. Identify procedures, tests and interventions performed exclusively for research purposes or more frequently than standard of care. Include alternative therapies, concurrent therapies discontinued per protocol, risk benefit ratio, and use of tissue/specimens. Discuss monitoring during washout periods if applicable. Include brief description of follow-up, if any.

Consent process and data collection will occur in a private room at the Duke Morreene Road Clinic or Duke brain Imaging Center or Duke Brain Stimulation Center in Red Zone of Duke South. All subjects

will sign an electronic single consent form uploaded to redcap or a printed hard copy. Any subject who wishes to sign their consent forms virtually, a blank consent form will be shared with subjects by redcap or emailed to them prior to the virtual visit. A phone or video visit will then be scheduled. At the virtual visit, an IRB approved study script will be used to review the research study with them for consenting purposes. The subject can then sign the consent form on redcap electronically or mail the signed hard copy to the study staff. The signed consent form will then be scanned and uploaded to Oncore and maestro care. Subjects can opt in or out of visits 2, and 3-5 of the research study.

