Writer's cramp behavioral data: Endpoints: Objective handwriting parameters of duration of writing, speed of handwriting, fluency of writing movements, axial pen pressure and interpretability of handwriting will be collected using a digital tablet and a pressure sensitive pen for data analysis. Additionally, an observer blinded to subject group will complete Writer's cramp rating scale(46) and BFM Rating Scale from video recordings of subjects performing each writing task (WT-1, WT-2 and WT-3). At the initial visit, patient's medical history will be collected to evaluate appropriateness of dystonia diagnosis. Patient will also be asked about the symptoms and signs of dystonia on rating scales including Adult dystonia and disability rating scale (ADDSD)(45) Burke Fahn Marsden Rating Scale (BFM) and Pain Scale to compare their baseline symptoms before and after all 4 visits.

Sample Size justification: A review of prior research studies employing TMS in writer's cramp and healthy volunteers measuring handwriting showed statistically significant effect sizes of 15-20% on various measures of writing performance using 6-12 subjects per group(38-40,43). A power analysis of our preliminary writing behavior data from 30 subjects in visit 1 demonstrated sample size of 60 in TMS for effect size of 30% with $\alpha = 0.05$. Assuming that I will be able to achieve similar sensitivity in writing metrics, I propose to study 20 patients in TMS group using writing task and fMRI as outcome measures for analysis (visit 1). Due to the pilot nature of fMRI and TMS stimulation parameters, the minimum number of subjects needed to calculate statistical power were selected. Therefore, in order to reach pilot data set of 20 patients in TMS group with 31% screening failure rate, we need approximately 70 FHD subjects. The 70 healthy volunteers will allow us to do a better statistical power analysis of clinical and fMRI outcomes measures to evaluate effect size for TMS As a result, we would like to increase our overall goal enrollment target to 140

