fMRI data: All image pre-processing will be implemented using the FSL program (<https://wiki.biac.duke.edu/biac:fsl>). Block design fMRI data will be extracted by time-series modeling using rectangular time windows for the motor task and rest periods. Group data will then be analyzed using GLM modeling. Any fMRI network identified in writing performance from previous fMRI research using the writing task in dystonia patients will be prospectively applied to the fMRI data of the subjects. Specifically, the imaging data from the pre and post fMRI sessions will be log transformed and subtracted from each other at each site in each subject. The global mean across sites will be subtracted from each log-transformed regional value, producing regional values normalized to each subject's global mean activity. In a second normalization, the mean for each site across subjects will be subtracted from each regional value. The result of these two normalizations is a subject x region matrix with the mean activity within and across subjects removed. This will be cross-correlated with the patterns previously found in order to quantify pattern expression for individual subjects in the present group. These individual subject pattern expressions will be entered into regressions predicting brain performance in order to verify that the patterns predict performance in new group. In addition, pattern expression will be used to predict rTMS effects on writing task performance (for example, differences in RT with active and sham rTMS).

Data & Safety Monitoring

- Summarize safety concerns, and describe the methods to monitor research subjects and their data to ensure their safety, including who will monitor the data, and the frequency of such monitoring. If a data monitoring committee will be used, describe its operation, including stopping rules and frequency of review, and if it is independent of the sponsor (per 45 CFR 46.111(a) (6)).

Safety monitoring: The subjects will be fully informed of the nature of the study requirements prior to enrollment and periodically throughout the study. The subject's well being will be continuously monitored by the experimenter, and the

Principal Investigator will report all serious adverse events in an expedited manner to the Duke University Health System (DUHS) Institutional Review Board (IRB) office and all applicable regulatory authorities in accordance with the Center's standard operating procedures.

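### Each patient is stimulated at two cortical sites to find the better target, but no planned analysis compares premotor with primary sensory cortex

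*Combined protocol and SAP*

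**What the plan says.** Background & Significance closes by giving the reason for stimulating two sites: "to evaluate the optimal cortical target for modulating putamen activity using TMS in WC subjects". The design follows from that. Under Purpose of the Study, for the 20 dystonia patients, "2 visits will involve active TMS and 1 visit will be sham TMS". In step 4 of Design & Procedures, "subjects will receive TMS at premotor cortex during one visit and at primary sensory cortex during the other active TMS visit". Visits are a week apart and fMRI follows each one, so every patient contributes a premotor, a primary sensory and a sham session.

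The paragraph Analysis and Statistics (Data Analysis & Statistical Considerations) plans two ANOVAs for visits 3-5:

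- The first has "groups (healthy vs dystonia) and stimulation type (task during vs after stimulation) as the main factor within subjects".
- The second crosses task timing with "treatment type (sham vs active) as the main factors between subjects for each handwriting measure".

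In the fMRI data paragraph, "Group data will then be analyzed using GLM modeling", with no contrasts listed. The one reference to a stimulation comparison there is an example, "differences in RT with active and sham rTMS".

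**The concern.** The design has three treatment conditions per patient and the analysis has two treatment levels. The distinction that drops out, between one active site and the other, is the one that the Background gives as the reason for stimulating both.

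Two things are at stake. First, a plan followed to the letter would yield no estimate of how the sites differ, either on putamen activity, which is the outcome named in the aim, or on handwriting. Second, if the two active visits enter the model as a single active level, a benefit confined to one site is averaged with a null result from the other. The trial could then report little difference from sham although one target works.

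**Working it through.** **Step 1: look for the site contrast.** Set against the stated aim, the analysis text offers:

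| Planned analysis | Factors or contrast stated | Compares the two sites? |
|---|---|---|
| First ANOVA, visits 3-5 | group; task during or after stimulation | no |
| Second ANOVA, visits 3-5 | task during or after stimulation; sham or active | no |
| fMRI group GLM | none stated | not stated |
| fMRI pattern expression predicting rTMS effects | active and sham, as an example | no |

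The fMRI paragraph does use the word site, but there it means regions of the image data, not the coil target. No premotor-versus-sensory comparison appears in any of the analysis text.

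**Step 2: what combining the active visits does to the signal.** Let each visit have variance s² and each pair of visits correlation rho (assumed equal across visits).

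- One site minus sham: variance 2·s²·(1−rho).
- Mean of both active visits minus sham: variance (1 + 1/2)·s²·(1−rho) = 1.5·s²·(1−rho).
- If the better site has effect D and the other has r·D, the combined effect is D·(1+r)/2.
- Combined standardised effect relative to one site against sham: (1+r)/2 × √(2/1.5) = (1+r)/2 × 1.155.

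This gives 0.577 for r = 0, 0.866 for r = 0.5 and 1.155 for r = 1.

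**Step 3: power.** Inputs:

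- n = 20, from the sample size justification ("I propose to study 20 patients in TMS group using writing task and fMRI as outcome measures for analysis").
- Two-sided alpha 0.05. The document gives 0.05 without sidedness; two-sided is assumed.
- Paired t-test with 19 degrees of freedom, noncentral t.
- dz, the better site's effect in units of the SD of one active-minus-sham difference. The documents give no SD, so dz is assumed. The value 0.66 is the one at which an uncorrected site-versus-sham test has 80% power with 20 patients; 0.5 and 0.8 show the range.

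The only power calculation in the document (60 for a 30% effect) states neither SD nor power. It cannot be reproduced or turned into a dz, and this point does not rest on it.

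| dz of better site | One site vs sham, alpha 0.05 | One site vs sham, alpha 0.025 (first Holm step) | Combined, other site inert | Combined, other site half | Combined, both equal |
|---|---|---|---|---|---|
| 0.5 | 56% | 44% | 23% | 45% | 69% |
| 0.66 | 80% | 70% | 37% | 68% | 90% |
| 0.8 | 92% | 86% | 50% | 84% | 98% |

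At dz 0.66 the combined standardised effects are 0.577 × 0.66 = 0.381, 0.866 × 0.66 = 0.572 and 1.155 × 0.66 = 0.762. Simulation of 40,000 trials at dz 0.66 gave 80.1% for one site against sham and 36.7% for the combined test with an inert second site, in agreement with the table.

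**Step 4: precision of the site contrast.** With 20 complete pairs, the 95% confidence interval for premotor minus primary sensory has half-width 2.093/√20 = 0.47 SDs of the paired difference. If the weaker site has half the effect, the true difference at dz 0.66 is 0.33 SDs, which is smaller than that half-width. The contrast is estimable but not sharply so.

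**The case against.** **Combining is inferred.** A reader might take it as settled that the plan averages the two active visits. The text does not say so. Sham versus active could be run once per site, with no dilution. That reading is not written down either, and two separate comparisons with sham would still not compare the sites. So the missing contrast stands on either reading; the dilution stands only on the plain one.

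**The 37% figure is one end of a range.** A reader might infer that combining the sites cuts power from 80% to 37%. That needs a wholly inert second site, whereas the Background cites support for both, and it sets an uncorrected test against the combined one. Against the Holm-step figure of 70%, combining roughly breaks even when the weaker site has half the effect (68%) and gains when both work equally (90%). It loses materially only when the weaker site has less than about half the effect.

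**The fMRI plan is open rather than restricted.** A reader might infer that the imaging analysis is confined to active versus sham. That phrase is only an example within the prediction of task performance, and an unspecified GLM does not exclude a site contrast. The plan fails to state one; it does not rule one out.

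**The target question is not the headline goal.** Purpose of the Study gives baseline differences, safety and feasibility as the goal. Step 6 of Design & Procedures assigns the visit 3-5 data to safety and feasibility, and the sample size text calls this a pilot. This stands: it is a gap between aim and analysis, not a failed confirmatory test. Nor are the data compromised, because each patient has a separate session per site and the contrast can be recovered. But item 6 of Data Storage and Management requires the statistical approach to be fixed beforehand and warns against data dredging, so the contrast should be written in before analysis.

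**Conclusion.** The point holds. The plan gives the choice between targets, judged on putamen activity, as the reason for stimulating two sites, and no written analysis makes that comparison for imaging or for handwriting. This needs no numerical assumption.

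The cost in power is conditional. If the two active visits are combined, and with 20 patients, dz 0.66, two-sided alpha 0.05 and equal variances and correlations, the combined test ranges from about 37% to 90% depending on how far the second site works, against about 70% for one site versus sham at the first Holm step. The documents do not support the stronger conclusion that combining necessarily weakens the trial, or that the collected data could not answer the target question.

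**What to change.** In Analysis and Statistics, replace the sham-or-active factor with a three-level within-patient factor: premotor, primary sensory, sham. This also removes the between-subjects label, which does not fit a design where every patient receives all three. Then pre-specify:

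1. Premotor minus primary sensory with its 95% confidence interval, first for putamen task activity on the post-TMS fMRI and then for handwriting.
2. Each site minus sham, with Holm across the two.
3. Pooled active minus sham, kept as a secondary estimate.

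State the same contrasts in the fMRI data paragraph, and say that at 20 patients the site contrast is a pilot estimate and not a powered test.

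The change is to wording only and needs no further patients, visits or scans. The price is some power: at dz 0.66, the Holm step takes one site versus sham from 80% to 70%, and if both sites work equally the pooled test's 90% is no longer the lead result.
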